5.6 Biomarker Assessments

Not applicable

5.7 Outcomes Research Assessments

Not applicable

5.8 Other Assessments

5.8.1 Diet and Exercise Counseling

Starting at entry into the lead-in period, subjects will be instructed on a diet and an exercise program in accordance with the ADA or similar local guidelines to be followed for the study duration.

A registered dietitian, registered nurse, physician, Certified Diabetes Educator (CDE), nutritionist, or other qualified member of the study team who has appropriate documented training, will provide this counseling.

5.8.2 Weight, Height, and BMI

Body weight and height will be measured according to the schedule presented in the study flow chart/time and event schedule (see Section 5.1) and will be recorded in the eCRF.

The study-site staff should use a digital precision scale if possible and record the weight to the first decimal point (e.g., 69.3 kg). The subject should wear a standard hospital-type gown or equivalent light indoor clothing, shoes removed, and bladder empty for the body weight measurement at each visit. Subjects should be weighed on the same scale at all visits.

Measurement of height should be performed with the subject's shoes removed. The subject's knees should be straightened, head held erect and eyes forward.

Body mass index is determined by weight (kg) divided by height (m) squared.

Method of BMI Calculation:

- Use actual height and weight
- To calculate BMI:
 - \circ Convert pounds (lbs) to kilograms (kg = lb / 2.2)
 - \circ Convert inches (in) to centimeters (cm = in X 2.54)
 - o BMI = (weight in kg) / (height in cm/100) 2
 - o Round to one decimal place (if 0.05 or greater, round up)

5.9 Results of Central Assessments

Blood and urine samples will be obtained at specified time points for laboratory evaluations (see Appendix 1). The central laboratory for this study will perform the analysis of all scheduled laboratory tests and will provide reference ranges for these tests. The central laboratory will provide specific instructions for collection, processing, packaging, and shipping of all samples.

The HbA1c values and urinary glucose values, including the urinary glucose:creatinine ratio will be blinded to the Sponsor, Investigator, site, and subject for the duration of the study following IP administration on Day 1 until after study completion. In the event of an HbA1c result > 8.0% during the LT period (when these values require subject rescue), the investigator will be informed via an HbA1c alert from the central laboratory, but will remain blinded to the HbA1c result. After study completion at Week 56 (and data locked and analysis completed), the above measurements will be unblinded and available to the Sponsor and Investigator.

6 ADVERSE EVENTS

An *Adverse Event (AE)* is defined as any new untoward medical occurrence or worsening of a preexisting medical condition in a clinical investigation subject administered study drug and that does not necessarily have a causal relationship with this treatment. An AE can therefore be any unfavorable and unintended sign (such as an abnormal laboratory finding), symptom, or disease temporally associated with the use of study drug, whether or not considered related to the study drug.

The causal relationship to study drug is determined by a physician and should be used to assess all AEs. The causal relationship can be one of the following:

- Related: There is a reasonable causal relationship between study drug administration and the AE.
- Not related: There is not a reasonable causal relationship between study drug administration and the AE.

The term "reasonable causal relationship" means there is evidence to suggest a causal relationship.

Revised Protocol No: 06

Adverse events can be spontaneously reported or elicited during open-ended questioning, examination, or evaluation of a subject. (In order to prevent reporting bias, subjects should not be questioned regarding the specific occurrence of one or more AEs.)

The Sponsor/designee will be reporting AEs to Regulatory Authorities and Ethics Committees according to local applicable laws including European Directive 2001/20/EC and Food and Drug Administration Code of Federal Regulations 21 CFR Parts 312 and 320.

Any AEs that are unresolved at the subject's last AE assessment or other assessment/visit as appropriate in the study are followed up by the Investigator for as long as medically indicated, but without further recording in the CRF. AstraZeneca retains the right to request additional information for any subject with ongoing AE(s)/SAE(s) at the end of the study, if judged necessary.

6.1 Serious Adverse Events

A Serious Adverse Event (SAE) is any untoward medical occurrence that at any dose:

- Results in death
- Is life-threatening (defined as an event in which the subject was at risk of death at the time of
 the event; it does not refer to an event which hypothetically might have caused death if it were
 more severe)
- Requires inpatient hospitalization or causes prolongation of existing hospitalization (see NOTE below)
- Results in persistent or significant disability/incapacity
- Is a congenital anomaly/birth defect
- Is an important medical event (defined as a medical event(s) that may not be immediately life-threatening or result in death or hospitalization but, based upon appropriate medical and scientific judgment, may jeopardize the subject or may require intervention [e.g., medical, surgical] to prevent one of the other serious outcomes listed in the definition above.) Examples of such events include, but are not limited to, intensive treatment in an emergency room or at home for allergic bronchospasm; blood dyscrasias or convulsions that do not result in hospitalization. Potential DILI is also considered an important medical event. (See Section 6.6 for the definition of potential DILI.)

Suspected transmission of an infectious agent (e.g., pathogenic or nonpathogenic) via the study drug is an SAE.

Although pregnancy, overdose, cancer, and DILI are not always serious by regulatory definition, these events must be handled as SAEs. (See Section 6.1.1 for reporting pregnancies).

Any component of a study endpoint that is considered related to study therapy (e.g., death is an endpoint, if death occurred due to anaphylaxis, anaphylaxis must be reported) should be reported as an SAE (see Section 6.1.1 for reporting details).

NOTE:

The following hospitalizations are not considered SAEs in this clinical study:

- A visit to the emergency room or other hospital department < 24 hours, that does not result in admission (unless considered an important medical or life-threatening event)
- Elective surgery, planned prior to signing consent
- Admissions as per protocol for a planned medical/surgical procedure
- Routine health assessment requiring admission for baseline/trending of health status (e.g., routine colonoscopy)
- Medical/surgical admission other than to remedy ill health and planned prior to entry into the study. Appropriate documentation is required in these cases
- Admission encountered for another life circumstance that carries no bearing on health status
 and requires no medical/surgical intervention (e.g., lack of housing, economic inadequacy,
 caregiver respite, family circumstances, administrative reason)
- Admission for administration of anticancer therapy in the absence of any other SAEs (applies to oncology protocols)

6.1.1 Serious Adverse Event Collection and Reporting

Following the subject's written consent to participate in the study, all SAEs, whether related or not related to study drug, must be collected, including those thought to be associated with protocol-specified procedures. All SAEs must be collected that occur during the screening period and within 28 days of discontinuation of dosing.

The investigator must report any SAE that occurs after these time periods and that is believed to be related to study drug or protocol-specified procedure.

Serious adverse events will also be collected quarterly from the Week 56 visit to the Week 104 post-study visit.

An SAE report must be completed for any event where doubt exists regarding its seriousness.

If the Investigator believes that an SAE is not related to study drug, but is potentially related to the conditions of the study (such as withdrawal of previous therapy or a complication of a study procedure), the relationship must be specified in the narrative section of the SAE Report Form.

Serious adverse events, whether related or not related to study drug, and pregnancies must be reported to Sponsor (or designee) within 24 hours of awareness of the event.

All SAEs will be recorded in the CRF. If any SAE occurs in the course of the study, then Investigators or other site personnel must inform the appropriate AstraZeneca representatives within one day i.e., immediately but **no later than 24 hours** of when he or she becomes aware of it.

The designated AstraZeneca representative will work with the Investigator to ensure that all the necessary information is provided to the AstraZeneca Patient Safety data entry site within 1 calendar day of initial receipt for fatal and life-threatening events and within 5 calendar days of initial receipt for all other SAEs.

For fatal or life-threatening AEs where important or relevant information is missing, active follow-up must be undertaken immediately. Investigators or other site personnel must inform AstraZeneca representatives of any follow-up information on a previously reported SAE within one calendar day i.e., immediately but **no later than 24 hours** of when he or she becomes aware of it.

Serious adverse events must be recorded on the SAE Report Form; pregnancies on a Pregnancy Surveillance Form (electronic or paper forms). The preferred method for SAE data reporting collection is through the eCRF. The paper SAE/pregnancy surveillance forms are only intended as a back-up option when the eCRF system is not functioning. In this case, the paper forms are to be transmitted via email or confirmed facsimile (fax) transmission to:

| SAE Email Address: |
|-----------------------|
| USA |
| SAE Telephone Number: |
| SAE Facsimile Number: |
| Other |
| SAE Facsimile Number: |
| SAE Telephone Number: |

For studies capturing SAEs through EDC, electronic submission is the required method for reporting. In the event the electronic system is unavailable for transmission, paper forms must be used and submitted immediately. When paper forms are used, the original paper forms are to remain on-site.

If only limited information is initially available, follow-up reports are required. (Note: Follow-up SAE reports must include the same investigator term(s) initially reported.)

If an ongoing SAE changes in its intensity or relationship to study drug or if new information becomes available, the SAE report must be updated and submitted within 24 hours to the Sponsor (or designee) using the same procedure used for transmitting the initial SAE report.

After the initial SAE report, the Investigator is required to proactively follow each subject at subsequent visits/contacts. All SAEs will be followed until resolution, stabilization, the event is otherwise explained, or the subject is lost to follow-up.

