d Visit may be scheduled at any time between Day -28 to +7 days of the original scheduled date to allow flexibility of scheduling.

Table 5.1-4: Early Treatment Discontinuation (ETD) Follow-up Non-Treatment Phase

| Procedure | Non- treatment Follow-up, up to and including Wk 26 Office Visit ^{a,b} | Non- treatment Follow-up, past Wk 26 and including Wk 52 Office Visit ^{a,b} | Non- treatment Follow-up Phone Assessment (Day 1 up to and including Wk 56) ^{b,c} | Quarterly between Wk 56 and Wk 104 | Wk 104 Post- study Visit ^c | Notes |
|--|--|--|--|---|--|---|
| Safety Assessments | | | | | | |
| Targeted physical examination | X | X | | | | |
| Vital signs | X | X | | | | |
| Body weight & height | X | X | | | X | |
| Review concomitant medications | X | X | X | | | |
| Serious Adverse Events Assessment | X | X | X | X* | X | *Assessed by Phone |
| Adverse Events Assessment | X | X | X | X* | X | *Assessed by Phone |
| Standard safety laboratory panel (Blood) | X | X | | | | Appendix 1 |
| Fasting Plasma Glucose (FPG) | X | X | | | | |
| HbA1c | X | X | | | | |
| Telephone reminder calls | | | | X | | |
| Tanner Staging | X* | X* | | | X | Appendix 3; *only at time points corresponding to originally scheduled Week 26 and Week 52 visits |
| Growth, bone and maturation markers | X | X | | | X | Thyroid-stimulating hormone (TSH), free thyroxine, luteinizing hormone (LH), follicle-stimulating hormone (FSH), estradiol, total testosterone, insulin-like growth factor-1 (IGF-1), insulin-like growth factor binding protein-3 (IGFBP-3), calcitonin, 25-hydroxy vitamin D, bone alkaline phosphatase, osteocalcin, parathyroid |

Table 5.1-4: Early Treatment Discontinuation (ETD) Follow-up Non-Treatment Phase

| Procedure | Non- treatment Follow-up, up to and including Wk 26 Office Visit ^{a,b} | Non- treatment Follow-up, past Wk 26 and including Wk 52 Office Visit ^{a,b} | Non- treatment Follow-up Phone Assessment (Day 1 up to and including Wk 56) ^{b,c} | Quarterly between Wk 56 and Wk 104 | Wk 104 Post- study Visit [©] | Notes |
|--------------------|--|--|--|---|--|--|
| Safety Assessments | | | | | | |
| | | | | | | hormone (PTH) and carboxyterminal cross-linked telopeptide of Type 1 collagen (CTX-1) |

^a In-office assessments to occur at time points corresponding to originally scheduled Day 1 to Week 26 (Short-term) and past Week 26 to Week 52 (Long-term) visits.

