3.4.1 Adverse events

AEs (serious and non-serious, excluding hypoglycaemic or DKA events that are not reported as SAEs) will be collected throughout the study up to Week 56, and will also be collected quarterly between Week 56 and Week 104 via phone assessment. Adverse events will be classified by system organ class (SOC) and preferred term (PT) according to the Medical Dictionary for Regulatory Activities (MedDRA), based on the MedDRA version current at the time of database lock. Each subject will be counted once within a SOC or PT in AE frequency tables, under the maximum intensity within each category. For summaries of AEs by relationship to study drug, as assessed by the investigator (related, not related), subjects will be counted under the most

related instance within each SOC or PT. For the summary of AEs that occurred in $\geq 5\%$ of the subjects within a treatment group (based on PTs) the number of AEs will also be presented.

Events will be considered treatment-emergent if:

- The event started on or after the first dose of IP (Day 1) and up to and including 4 days for AEs and 30 days for SAEs after the last dose date.
- The event started before Day 1 but increased in intensity or relatedness to study medication on or after Day 1.
- The event onset date is missing or partial (unless the stop date of the event indicates that the event cannot be treatment emergent).
- Events will be considered treatment emergent unless they can be proven not to be so from the data.

Details for handling of missing and partial event dates for determining treatment emergence are provided in the Appendix (Section 8.2).

Listings will include the AE duration, calculated as AE stop date - AE start date + 1. AE duration will be calculated only when complete dates (at least day, month, year) for the start and stop date are provided. Each AE will be graded for intensity (mild, moderate, severe). If intensity is missing, the event will be regarded as severe. Each AE will also be assessed for relationship to the study drug (related, not related). Adverse events with missing relationship to study drug will be considered treatment-related for the purpose of summarising AEs related to study drug. Adverse events with missing flag indicating serious will be considered serious for AE summaries.

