The following descriptive summaries will also be provided for the ST, ST+LT and randomised withdrawal period, regardless of rescue medication initiation, for:

- Any AE by SOC, PT and maximum intensity (mild, moderate, severe).
- Any AE related to study drug (not related, related [including AEs with missing relationship to study drug]) by SOC and PT.
- Any AE by SOC and PT for common PTs (defined as PTs reported by $\geq 5\%$ of the subjects in any treatment group within the period). Number of events (and incidence rate for the ST+LT period) will also be presented.
- Any non-serious AE by SOC and PT

Summaries of AEs by SOC and PT will be provided by treatment group for the ST, ST+LT and randomised withdrawal period, regardless of rescue medication initiation, for the following subgroups:

- Age group using the randomisation strata (≥ 10 and < 15 years, ≥ 15 and < 18 years)
- Sex (male, female)
- Race (white, non-white)
- Baseline antidiabetic treatment (metformin only, insulin only, combination of metformin and insulin)

with age, sex and baseline antidiabetic treatment category being defined based on randomisation strata.

The ST+LT period presentations for Any AE by SOC and PT and Any AE by SOC and PT for common PTs will also be presented for the subgroup of subjects on a stable baseline dose of metformin IR or XR (with or without insulin).

In addition, AEs not included in the ST+LT analysis period per [Table 8](#) and those AEs reported quarterly between Week 56 and Week 104 will also be summarised for the post-study visit at Week 104.

No formal comparisons are made between treatments. No formal statistical testing will be performed, only summary statistics are provided.

A listing of all reported AEs falling into the ST+LT period will be produced. A separate listing will be provided for all AEs during the study.

Adverse events of special interest

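### Protocol 6.1.1 contradicts itself, the visit schedule and the SAP on how long all SAEs must be collected after study drug stops

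*Protocol*

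**What the plan says.** Protocol Section 6.1.1 contains two kinds of rule.

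- **Restrictive.** "All SAEs must be collected that occur during the screening period and within 28 days of discontinuation of dosing". The sentence that follows reads: "The investigator must report any SAE that occurs after these time periods and that is believed to be related to study drug or protocol-specified procedure".
- **All-cause.** The section opens by saying that, after consent, "all SAEs, whether related or not related to study drug, must be collected", with no end date. It later says that every SAE goes into the CRF and that any SAE arising during the study must be notified within 24 hours. It also provides: "Serious adverse events will also be collected quarterly from the Week 56 visit to the Week 104 post-study visit".

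The rest of the plan follows the all-cause reading.

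- Protocol Section 3.7 keeps children who stop study drug early in the study and in follow-up.
- Protocol Table 5.1-4, written for these children, has the row "Serious Adverse Events Assessment | X | X | X | X* | X | *Assessed by Phone". All five columns are marked: office visits to Week 26, office visits to Week 52, phone contacts to Week 56, quarterly contacts, and Week 104. Nothing limits the assessment to related events. SAP Table 16 repeats the schedule.
- SAP Section 3.4.1 says that AEs, serious and non-serious, "will be collected throughout the study up to Week 56" and then quarterly to Week 104. It defines treatment-emergent events as those starting "up to and including 4 days for AEs and 30 days for SAEs after the last dose date".
- SAP Section 4.7.1.1 adds that AEs outside the ST+LT window and "those AEs reported quarterly between Week 56 and Week 104 will also be summarised for the post-study visit at Week 104". Section 4.7.1.3 summarises SAEs at Week 104 and lists post-treatment SAEs.

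**The concern.** The schedule tells a site when to ask about SAEs, while Section 6.1.1 tells it which ones must be collected. A site can make every scheduled contact, hear of an SAE that it judges unrelated, and still find in 6.1.1 a sentence under which it need not be reported. Another site, reading the opening sentence, would report the same event. For children who stop drug early, the late SAE record could then mix complete reporting with reporting filtered by the investigator's opinion on causality.

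The events concerned are not trivial. Section 6.1 requires cancer, drug-induced liver injury, overdose and pregnancy to be handled as SAEs. Section 6.8.1 sends serious adverse events of interest, including malignancies, fractures and ketoacidosis, through the 6.1.1 rules. Section 6.2.1 sets no 28-day limit for non-serious events, so on paper the serious events have the narrower rule.

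**Working it through.** The plan gives no figure to reproduce. The check is calendar arithmetic plus a comparison of the texts.

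**Inputs.** All-cause window of 28 days after dosing stops (Protocol 6.1.1); treatment-emergent SAE window of 30 days (SAP 3.4.1, and SAE cut-offs in SAP Table 8); quarterly SAE collection from Week 56 (Protocol 6.1.1); contact weeks from Protocol Tables 5.1-2 and 5.1-3, carried into Table 5.1-4.

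**Formulas.** Nominal day = 7 × week + 1, so Week 56 is day 393. End of the 28-day window = last-dose day + 28. Interval under the restrictive sentences alone = 393 − window end.

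| Last dose at | Day | 28-day window ends | Interval to Week 56 |
|---|---|---|---|
| Week 6 | 43 | 71 | 322 days = 46 weeks |
| Week 12 | 85 | 113 | 280 days = 40 weeks |
| Week 26 | 183 | 211 | 182 days = 26 weeks |
| Week 40 | 281 | 309 | 84 days = 12 weeks |
| Week 52 | 365 | 393 | 0 |

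**Completers.** The 28-day window ends on day 393, the nominal Week 56 contact. Days 29 and 30 (days 394 and 395) fall in the quarterly period, so there is no gap on the nominal schedule.

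**Contacts for early stoppers.** From Week 12 the nominal contacts are at Weeks 12, 14, 20, 26, 32, 36, 40, 46, 52 and 56. The spacings are 2, 6, 6, 6, 4, 4, 6, 6 and 4 weeks, so SAE assessments are at most 6 weeks apart throughout the intervals in the table.

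**Exposure of the main SAE tables.** Only treatment-emergent SAEs enter, and these stop at 30 days after the last dose. The part beyond the protocol's window is 30 − 28 = 2 days, or 2/30 = 6.7% of the post-dose window. SAEs later in the intervals above are outside those tables by design. They belong to the Week 104 summaries and the listings.

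**Related detail.** SAP Section 4.1.7.1 gives Week 56 a target day of 395, which is 365 + 30, whereas 7 × 56 + 1 = 393 is 365 + 28. The same 28/30-day split appears there.

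**The case against.** The strongest reply is that the restrictive sentences should not be read alone. Section 6.1.1 itself demands all SAEs after consent, CRF entry of every SAE, and 24-hour notification of any SAE during the study. Early stoppers remain in the study, and Table 5.1-4 schedules their SAE assessments to Week 104. The document history says that Amendment 04 clarified AE and SAE collection to study completion. On this view the 28-day sentence is a leftover and most sites would report everything.

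Much of that stands. It shows that the intent is all-cause collection and that contact is maintained. It does not remove the conflict. The restrictive sentences are operative reporting rules, the second deals expressly with events after the 28 days, and nothing says which rule prevails.

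A reader might infer from the table of intervals that early stoppers have a gap of many months in SAE coverage, and convert it into child-years lost. The documents do not support this. SAE assessments are scheduled throughout those intervals, and the documents give neither a discontinuation rate nor an SAE rate from which a number of lost events could follow.

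A reader might also infer that the comparison between arms is distorted. That would need different stopping rates by arm, which the documents do not give. The main tables are also cut at 30 days, and the AE summaries are descriptive, without formal tests.

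**Conclusion.** The inconsistency is real and modest. Section 6.1.1 ends mandatory all-cause SAE collection at 28 days in one sentence and requires it without limit in others. The schedule and the SAP follow the unlimited version, and the SAP's treatment-emergent window is 2 days longer than the protocol's.

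Unrelated SAEs in children who stop drug early could be omitted if a site applies the restrictive sentences literally. This would touch days 29 and 30 of the treatment-emergent SAE tables, and also the Week 104 SAE summaries and the SAE listings. The effect on the main tables is small. These conclusions assume nominal visit timing; Table 5.1-3 allows the Week 56 contact to move by 7 days either way. How sites actually read 6.1.1 cannot be known from the documents.

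**What to change.** Reconcile Section 6.1.1 with Tables 5.1-3 and 5.1-4 and SAP Section 3.4.1. Replace the 28-day sentence with a statement that all SAEs, related or not, are collected from written consent through the Week 104 visit or last contact, regardless of when study drug stopped. The sentence on later SAEs believed related would then apply only after that point. This also covers the SAP's 30-day window, which need not change. The SAP's Week 56 target day (395 against 393) should be reconciled at the same time.

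The cost is wording and site notification. No contacts are added, because the assessments are already scheduled; a few more SAE reports would have to be processed. If follow-up is too far advanced for an amendment to help, the sponsor should check how sites applied the rule to early stoppers and say so in the clinical study report.
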